7.3.6.2 Response for Non-Target Lesions

All lesions that are not selected as target lesions are defined as non-target lesions. Only three response categories will be defined.

The scale for non-target lesions response assessment as listed in [Table 7-8](#).

Table 7-8 Scale for Response Assessment of Non-Target Lesions

Score	Response Category	Criterion

-1	Worsened	Overall color increased by 1 grade or overall size/extent increased by 20% or new lesions
0	Not worsened, not remarkable improvement	
1	Remarkable improvement	Overall color decreased by at least 2 grades and overall size/extent decreased by 75%

7.3.6.3 Overall Response for Target and Non-Target Lesions

Before assessment, the investigator should add the scores from both target and non-target lesions evaluation. Overall response for Target and Non-Target lesions can be performed using the following scale in [Table 7-9](#).

Table 7-9 Scale for Overall Response Assessment

Score	Response Category
-1 or less	Worsened
0	Unchanged
1	Slight improvement
2	Moderate improvement
3 or more	Remarkable improvement

All measurements and scoring will be performed by investigator at each post-screening visit. At the baseline visit, only the measurements will be taken for comparison.

7.3.7 Independent Review Committee (IRC) on Photograph Assessment

7.3.7.1 Members of the IRC

Independently of the assessment of IGA and Modified Nobel Scoring System by the investigator, an independent review committee will blindly assess and judge the status of each lesion from the medical and technical viewpoints, using the photographs of the skin lesions of individual subjects collected from investigational sites. The independent review committee members will be blinded

to treatment assignment. The members of the IRC will consist of two dermatologists who are independent from persons involved in the sponsorship or the conduct of the study, such as the investigator, sub-investigators, study collaborators, coordinating investigators, medical experts, and the sponsor, and who treat patients with angiofibroma in everyday practice and have no direct conflict of interest with the sponsor. In the event there is a discrepancy between the two members of the IRC, a third dermatologist will perform adjudication and select dermatologist 1 or dermatologist 2.

7.3.7.2 Transmission, Control, Compensation, Masking, and Checking of Image Files

Canfield Scientific, Inc. will be responsible for transmission, control, compensation, masking, and checking of image files and will supply a written Work Instruction detailing the specific Photographic Review process in separate document. In accordance with separately prepared written procedures, the investigator or study collaborators will take the photographs of each lesion with provided label and color panel, mask images in the image files of the photographs if necessary, and transmit the image files to the CRO in charge of the control and compensation of the image files via a dedicated server. In accordance with separately prepared written procedures, the CRO in charge of the control and compensation of the image files will check, retain, and control the photographic image files stored on the dedicated server and store the image files that were compensated for color tone in the prescribed location on the dedicated server. The sponsor will periodically access the dedicated server as appropriate and ascertain if photographing and the transfer, retention, control, compensation, etc., of image files are being performed appropriately.

7.3.7.3 IRC

The sponsor, the CRO in charge of the control and disposition of image files, and the members of the IRC will hold meetings of the IRC in accordance with the written procedure for holding meetings of the IRC, which is separately prepared.

7.4 Assessment of Safety

7.4.1 Adverse Events

7.4.1.1 Adverse Events Assessments

An adverse event (AE) is an untoward medical occurrence in any subject during the study which does not necessarily have a causal relationship with the study drug treatment. Adverse events can be categorized as treatment-emergent or treatment-related. All AEs will be recorded and will be documented in the CRFs.

AEs will be collected from the time the subject signs informed consent/assent until 30 days after the last investigational product administration. Serious adverse events (SAEs) must be reported to the sponsor within 24 hours of awareness. The condition of the subject will be monitored

throughout the study for any signs or symptoms. The occurrence of AEs should be sought by nondirective questioning of the subject at each visit during the study. All AEs will be collected as:

- The subject's positive response to questions about their health.
- Symptoms spontaneously reported by the subject.
- Clinically relevant changes and abnormalities observed by the investigator (e.g., local and systemic tolerability, laboratory measurements, results of physical examinations, monitoring for infections and noninfectious pneumonitis).

If an AE worsens in intensity, it should be recorded as a new AE. Otherwise, it continues as the first report (counted as the same AE) until the subject is recovered.

The investigator or designee will record the following on the AE CRF:

- Adverse event and relevant clinical findings
- Time/date of onset
- Time/date of recovery
- Intensity
- Action taken on study drug/treatment
- Other action taken to treat the event
- Relation to study drug/treatment
- Seriousness of the AE

Adverse events requiring therapy must be treated with recognized standards of medical care to protect the health and well-being of the subject. Treatment due to an AE will be recorded.

All AEs with moderate or greater intensity and/or possibly or probably related to the study drug(s) or study procedure must be followed by the investigator until it is resolved or until the medical condition of the subject is stable; all relevant follow-up information will be reported to the sponsor.

The outcome of an AE will be classified as recovered/resolved, recovered/resolved with sequelae, recovering/resolving, not recovered/not resolved, fatal or unknown.

Safety assessment will include assessment of local safety (e.g., through active assessment of local signs and symptoms, such as scaling, itching etc.) as well as systemic safety. If a subject experiences a generalized rash or other health issue in the treatment area, the subject (or

parent/guardian) should contact the study site and the subject should report to the study center for examination.

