Planned Dates of Study:	5 Feb 2018 to 31 Dec 2021

Table 1-1 Visit Schedule and Assessments

Examination	Visit 1	Visit 2	Visit 3	Blinded Phase		Open-label Phase			Telephone End of Study (EOS)	Early Termination
	Screening	Baseline	Week 4	Telephone Visit 4	Visit 5	Visit 6	Telephone Visit 7	Visit 8		
	Up to Day -28	Day 1	Day 28 ± 7 d	Day 56 ± 7 d	Day 84 ± 7 d	Day 112 ± 7 d	Day 140 ± 7 d	Day 168 ± 7 d		
Informed consent/assent	X									
Photographic consent/assent										
Inclusion/exclusion criteria	X	X			X ^b					
Demographics/background information	X									
Medical history	X	X								
Prior and concomitant medication assessment	X	X	X	X	X	X	X	X	X	X
Physical examination	X							X		X
Vital signs	X	X	X		X	X		X		X
Samples (blood and urine) for clinical laboratory assessment	X		X		X	X		X		X
Pharmacokinetics			X							
Urine pregnancy test, if applicable ^c	X	X	X		X	X		X		X
Randomization		X								
Weigh study product; dispense to subject		X	X		X	X				

Examination			Blinded Phase			Open-label Phase			Telephone End of Study (EOS)	Early Termination
	Visit 1	Visit 2	Visit 3	Telephone Visit 4	Visit 5	Visit 6	Telephone Visit 7	Visit 8		
	Screening	Baseline	Week 4	Week 8	Week 12 (EOT DB)	Week 16	Week 20	Week 24 (EOT OL)		
Up to Day -28	Day 1	Day 28 ± 7 d	Day 56 ± 7 d	Day 84 ± 7 d	Day 112 ± 7 d	Day 140 ± 7 d	Day 168 ± 7 d	14 ± 3 days after final dose of IP ^a		
Dispense subject diary		X	X		X	X				
IGA	X	X	X		X	X		X		X
FASI (assessment of erythema, size, extension)	X	X	X		X			X		X
Modified Nobel Scoring System		X	X		X	X		X		X
Lesion count	X	X	X		X			X		X
Assessment of lesion elevation	X	X	X		X			X		X
Photography	X	X	X		X	X		X		X
Subject self-assessment survey	X	X	X		X	X		X		X
Collect used study medication; weigh the medication tube			X	Query Compliance	X	X	Query Compliance	X		X
Review subject diary			X	Query Compliance	X	X	Query Compliance	X		X
Record adverse events	X	X	X	X	X	X	X	X		X

EOT = End of Treatment; EOS = End of Study; DB = Double-blind; OL = Open-label; IGA = Investigator's Global Assessment; FASI = Facial Angiofibromas Severity Index; IP = Investigational product.

a: Subjects who do not enter the open-label phase of the trial will complete the End of Study visit 14 ± 3 days after the final double-blind dose at Visit 5 (Week 12). Subjects who do enter the open-label phase of the trial will complete the End of Study visit 14 ± 3 days after the final open-label dose at Visit 8 (Week 24).

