7.2.4.3 Visit 8 (Week 24 ± 7 days)

- Collect and review the dosing diary.
- Collect all study materials from the subject (or parent/guardian), including unused study medication, etc.
- Weigh the used tubes of study medication collected from the subject (or parent/guardian).
- Review any concomitant medication used since the previous study visit.
- Perform a physical examination, including height and weight.
- Measure vital signs (systolic and diastolic blood pressure, heart rate, and respiratory rate) with subject in a seated position.
- Obtain blood samples and optional urine samples for a laboratory profile including hematology, clinical chemistry, and urinalysis.
- Perform a UPT for females of childbearing potential. Remind sexually-active female subjects of childbearing potential to use approved method(s) of contraception. Remind sexually active male subjects that they (or their female partners) should use appropriate contraception. (In the unlikely event that a urine pregnancy test cannot be obtained, a serum pregnancy test can be run from the serum sample collected.) (For China, different pregnancy test procedure would be followed).
- Perform the following efficacy assessments:
 - Investigator's Global Assessment (IGA);
 - Facial Angiofibroma Severity Index (FASI) (assessment of erythema, size, and extension);
 - Modified Nobel Scoring System (assessment of target lesions and non-target lesions response);
 - Categorical lesion count using the following categories: (0) no lesion; (1) <25 lesions; (2) 25-50 lesions; (3) 51-75 lesions; (4) >75 lesions;
 - Assessment of lesion elevation.
- Take a photograph of the angiofibroma according to the Standardized Operation Procedure (Appendix 2).
- Have the subject (or parent/guardian for subjects under the developmental age of 7 years) complete the subject self-assessment survey.
- Record any AEs.

- Schedule the End of Study Visit.

7.2.5 Telephone End of Study Visit (14 ± 3 days after final dose of IP) – Both Blinded and Open-Label Participants

- Review any concomitant medication used since the previous study visit.
- Record any AEs.
- Inform Subjects that they may be approached to participate in future trials with this product.
- Dismiss the subject from the study.

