7.2.6 Early Termination (Blinded and Open-Label)

If a subject withdraws from the study prior to the End of Study visit, the subject is to return to the site. The early termination procedures should be performed, as specified below:

- Collect all study materials from the subject (or parent/guardian), including used and unused study medication, subject dosing diary, etc.
- Weigh the used tubes of study medication collected from the subject.
- Review any concomitant medication used since the previous study visit.
- Perform a physical examination, including height and weight.
- Measure vital signs (systolic and diastolic blood pressure, heart rate, and respiratory rate) with subject in a seated position.
- Obtain blood samples and optional urine samples for a laboratory profile including hematology, clinical chemistry, and urinalysis.
- Perform a UPT for females of childbearing potential. Remind sexually-active female subjects of childbearing potential to use approved method(s) of contraception. Remind sexually active male subjects that they (or their female partners) should use appropriate contraception. (In the unlikely event that a urine pregnancy test cannot be obtained, a serum pregnancy test can be run from the serum sample collected.) (For China, different pregnancy test procedure would be followed).
- Perform the following efficacy assessments:
 - Investigator's Global Assessment (IGA);
 - Facial Angiofibroma Severity Index (FASI) (assessment of erythema, size, and extension);
 - Modified Nobel Scoring System (assessment of target lesions and non-target lesions response);

- Categorical lesion count using the following categories: (0) no lesion; (1) <25 lesions; (2) 25-50 lesions; (3) 51-75 lesions; (4) >75 lesions;
- Assessment of lesion elevation.
- Have the subject (or parent/guardian for subjects under the developmental age of 7 years) complete the subject self-assessment survey.
- Take a photograph of the angiofibroma according to the Standardized Operation Procedure (Appendix 2).
- Record any AEs.
- Inform Subjects that they may be approached to participate in future trials with this product.
- Dismiss the subject from the study.

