7.4.2 Serious Adverse Events

A serious adverse event (SAE) is any untoward medical occurrence that at any dose:

- is life-threatening
- results in death
- requires in-patient hospitalization or prolongation of existing hospitalization
- results in persistent or significant disability/incapacity
- is a congenital anomaly/birth defect

- is an important medical event.

The death of a subject enrolled in a study is per se not an event, but an outcome. Any event resulting in a fatal outcome must be fully documented and reported, regardless of the causality relationship to the investigational product.

The term life-threatening refers to an AE in which the subject was at immediate risk of death at the time of the event. It does not refer to an event, which may have caused death, if it was more severe.

Medical and scientific judgment should be exercised in deciding whether expedited reporting is appropriate in other situations, such as important medical events that may not be immediately life-threatening or result in death or hospitalization but may jeopardize the subject or may require intervention to prevent one of the other outcomes listed in the definition above. These should also usually be considered serious. Examples of important medical events include AEs, which suggest a significant hazard, contraindication or precaution, occurrence of malignancy, or development of drug dependency or drug abuse.

Any SAE, whether or not deemed drug-related or expected, must be reported immediately to the sponsor or designee via email as soon as it becomes known to the investigator and not later than within 24 hours of his/her knowledge of the occurrence of an SAE. The investigator will document such events in the best possible detail on the SAE Report Form to be transmitted by email. SAEs will be collected from the time the subject signs informed consent/assent until 30 days after the last investigational product administration.

A pre-scheduled elective procedure is not to be considered an SAE, even if the subject is hospitalized, provided the condition requiring the pre-scheduled elective procedure was present before and did not worsen or progress between the subject's consent to participate in the study and the time of the procedure. In addition, the pre-scheduled elective procedure must be the sole reason for admission and intervention. An adverse event occurring during the pre-scheduled elective procedure should be recorded as an AE or SAE.

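### AEs and SAEs are to be collected to 30 days after the last dose, but the last scheduled contact is a call at 14 ± 3 days or an undated termination visit, so new events late in the window may be missed

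*Combined protocol and SAP*

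**What the plan says.** **The window.** For adverse events, section 7.4.1.1 states: "AEs will be collected from the time the subject signs informed consent/assent until 30 days after the last investigational product administration". Section 7.4.2 repeats the limit for serious events: "SAEs will be collected from the time the subject signs informed consent/assent until 30 days after the last investigational product administration".

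**How events are sought.** Section 7.4.1.1 ties active questioning to visits: "The occurrence of AEs should be sought by nondirective questioning of the subject at each visit during the study". Section 7.4.1.2 likewise places AE assessment at the study visits. Spontaneous reports and changes that the investigator observes are also accepted sources (7.4.1.1).

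**The last contact for completers.** Section 7.2.5 is headed "Telephone End of Study Visit (14 ± 3 days after final dose of IP"). Footnote a to Table 1-1 applies the same timing to both groups. Subjects who do not go on to open label "will complete the End of Study visit 14 ± 3 days after the final double-blind dose at Visit 5 (Week 12"), and those who do "will complete the End of Study visit 14 ± 3 days after the final open-label dose at Visit 8 (Week 24"). AEs are recorded at this call, and its last listed step is "Dismiss the subject from the study".

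**The last contact for early terminators.** Section 7.2.6 says: "If a subject withdraws from the study prior to the End of Study visit, the subject is to return to the site". AEs are recorded there too. No day relative to the last dose is given, no later call is listed, and the final step is the same dismissal.

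**The stated length.** The synopsis and section 4.1 count 2 weeks of follow-up within a maximum of about 30 weeks per subject.

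**The concern.** The stated collection window is longer than the contact schedule that feeds it. Once a subject has been dismissed, no readable section plans any further search for new events. The routes that remain are:

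- a spontaneous report;
- a subject or parent who makes contact about a rash or a reaction in the treatment area (7.4.1.1, 7.4.1.6);
- for subjects who refuse further participation after dosing, unspecified advice on follow-up safety investigations (5.4);
- an incidental finding while something already known is being followed, such as an existing AE or SAE, an abnormal laboratory value or a pregnancy (5.4, 7.4.1.1, 7.4.1.7, 7.4.4, 7.4.5, 13.2.2).

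Safety is part of the single study objective (3.0), and section 8.6.1 tabulates AE incidence as the percentage of subjects reporting an event. A reader of those tables would take them to cover 30 days after dosing, although about half of that period has no planned contact. Section 7.4.1.1 also defines an AE as an occurrence during the study, while subjects leave the study before day 30. With up to 15 sites planned, sites could differ on whether they should contact a dismissed subject, or record an event that starts on, say, day 20.

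**Working it through.** **1. Reproduce the stated duration.** Inputs from the synopsis and 4.1: screening 4 weeks, blinded 12, open label 12, follow-up 2.

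4 + 12 + 12 + 2 = 30 weeks, or 28 + 84 + 84 + 14 = 210 days.

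The plan's figure is reproduced with 2 weeks of follow-up. With 30 days instead, the sum is 28 + 84 + 84 + 30 = 226 days, and 226 / 7 = 32.3 weeks. The schedule was therefore built on the 2-week follow-up.

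**2. Completers.** Inputs: window of 30 days (7.4.1.1, 7.4.2); call on day 14 ± 3 (7.2.5). Days without a scheduled contact = 30 − day of call.

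| Day of call | Days left | Share of window |
|---|---|---|
| 17 | 30 − 17 = 13 | 13/30 = 43% |
| 14 | 30 − 14 = 16 | 16/30 = 53% |
| 11 | 30 − 11 = 19 | 19/30 = 63% |

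**3. Early terminators.** Let t be the day of the termination visit after the last dose. The gap is 30 − t. The documents do not fix t, so these values are assumptions:

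- t = 0 gives 30 days;
- t = 7 gives 23 days;
- t = 11 to 17 gives 19 to 13 days, the same range as for completers.

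The gap exceeds the completers' range only if t is below 11.

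**4. Which subjects are affected in the blinded comparison.** Subjects who enter open label are still questioned at Visits 6 to 8. Visit 7 is planned for Day 140 and Visit 5 for Day 84, a difference of 56 days. With both 7-day windows at their extremes it is 133 − 91 = 42 days. An open-label subject who reaches Visit 7 has therefore been questioned more than 30 days after the last blinded dose. For the 12-week blinded treatment, the gap concerns completers who do not enter open label and subjects who terminate during the blinded phase. For open-label entrants it falls after their last open-label dose.

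**The case against.** **The plan can be operated as written.** Spontaneous reports are a listed source, and no section promises active questioning to day 30. That stands. A reader might infer a flat contradiction between the 30-day window and the day-14 call, but an unsolicited event on day 25 can still be recorded. The mismatch is in solicitation.

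**No loss is shown.** This also stands. The figures are calendar days. The documents give no rate of late events, and they expect systemic exposure to be very low (2.2, 2.5, Appendix 1). That expectation lowers the likely importance of the gap but is not evidence that late events will be absent.

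**Other routes exist.** They do, and some subjects will stay in contact past their last visit. Under section 7.4.5, a subject who becomes pregnant stops treatment but continues with follow-up visits, so neither formula above fits that path. But these routes serve known conditions. They do not reach a subject who leaves with nothing outstanding and develops something new.

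**Some subjects cannot be contacted later.** Section 5.4 ends participation at once on request, so a later call may be impossible for part of the early-termination group whatever the protocol says.

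**Some text cannot be judged.** The consent pages and the opening of section 13.2, on reporting SAEs and pregnancies, are not in the public text. They may tell subjects or sites something about reporting to day 30.

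**The Table 1-1 cell.** The AE row appears blank under the End of Study call, and a reader might infer that AE recording stops at Visit 5 or Visit 8. Section 7.2.5 expressly lists AE recording at that call, and table cells may have been damaged in conversion from PDF, so the point does not rest on this.

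**Conclusion.** The point holds as a minor mismatch between the stated AE and SAE window and the scheduled contacts. For completers, 13 to 19 of the 30 days (16 nominal) have no planned AE questioning. For early terminators the number depends on a visit day that the plan does not set. Ascertainment of new-onset events over the stated window may therefore be incomplete.

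Two stronger conclusions are tempting and unsupported:

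- *Bias between arms.* The contact rules are the same in every arm, and nothing in the documents shows that reporting after dismissal would differ by treatment. The Week 12 efficacy endpoint does not use these data.
- *Early terminators are always covered less well.* That is true only if the termination visit falls before day 11.

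Confidence is high on the timing mismatch and lower on its practical consequence. The verdict assumes that no contact after the End of Study call or the termination visit is scheduled in the text that cannot be seen.

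**What to change.** Reconcile the 30-day window (7.4.1.1, 7.4.2) with the last scheduled contact on each exit path (7.2.5, 7.2.6, Table 1-1 and its footnote a), and with the 2-week follow-up and approximate 30-week duration in the synopsis and 4.1. The aim is that the period over which AEs are reported is the period over which subjects are contacted. For early termination, this requires the timing of the last contact to be stated relative to the last dose. The sponsor decides which figure stands. A sentence saying only that late collection is unsolicited would describe the gap without closing it.

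The cost is low. Changing the window or the contacts is hard to call administrative, so a written amendment under 9.1 is likely. Section 12.2 asks for IRB/IEC approval of any amendment that is not administrative. If the later date stands, there is also one more telephone contact and a nominal maximum of about 32 weeks. If the earlier date stands, the 30 weeks are unchanged.
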